8.4.11 Treatment Compliance

Study medication will be dispensed at clinic visits and re-supplies of study drug may be shipped in temperature-controlled containers to the subject's home. All unused study drug received by the subjects since the previous visit will be returned at the subsequent visit for drug accountability.

An inventory of the study medication supplies will be performed by the site or authorized study designee and recorded onto the Drug Accountability Log in the subject's source document records or equivalent.

8.5 Efficacy and Safety Variables

The Schedule of Assessments was previously provided in [Section 2.1](#).

8.5.1 Efficacy Variables

Efficacy will be assessed using the Friedreich's Ataxia Rating Scale (FARS) (total score [FARStot] and score excluding the peripheral nervous system subscale score and the facial and tongue atrophy and fasciculations from the bulbar subscale score [FARS-mNeuro score]).

8.5.1.1 Friedreich's Ataxia Rating Scale (FARS)

The FARS will be performed at the EOS (or PW) Visit. The FARS includes neurological signs that specifically reflect neural substrates affected in FA. Based on a neurological examination, bulbar, upper limb, lower limb, peripheral nerve, and upright stability/gait functions are assessed [Friedman et al, 2010; Lynch et al, 2006; Subramony et al, 2005].

The FARStot score has a maximum of 125 points (see assessment in [Section 16.3](#)), and the FARS-mNeuro score has a maximum of 93 points.

8.5.2 Safety Variables

Safety assessments will include adverse event monitoring, concomitant medication monitoring, physical examinations, vital signs, ECGs, clinical safety laboratory evaluations (complete blood count, chemistry, and urinalysis), and pregnancy testing (if applicable).

8.5.2.1 Adverse Events

Comprehensive assessments of any apparent adverse event experienced by the subject will be performed throughout the course of this study. Study center personnel will record all adverse events, whether observed by the Investigator/designee or reported by the subject/caregiver, in the source document and on the eCRF. A physician (the Principal Investigator or a physician/nurse practitioner/physician's assistant designated by the Principal Investigator) will manage and treat any treatment-emergent adverse event (TEAE).

Adverse event information will be elicited from each subject/caregiver by indirect questioning using a non-leading question, such as "Has anything bothered you since your last visit or is anything bothering you now?" Adverse event data also may be volunteered by the parent/caregiver to the Investigator (or designee). A physician (either the Principal Investigator or a physician/nurse practitioner/physician's assistant designated by the Principal Investigator) will assess the seriousness, severity, and causality of each adverse event based on the following definitions and documentation requirements.

8.5.2.1.1 Definitions

Adverse Event: As defined by the ICH, an adverse event is any untoward medical occurrence in a patient or clinical investigation subject administered an investigational product, whether or not the event is considered related to the investigational product. An AE is therefore any unfavorable and unintended sign (including an abnormal laboratory finding), symptom, or disease (new or exacerbated) temporally associated with the use of the investigational product.

NOTE: The term "adverse event" includes both non-serious and serious adverse events unless otherwise specified

A TEAE is any adverse change from the subject's baseline condition, including any laboratory test value abnormality judged as clinically significant by the investigator, that occurs on or after the date of the first dose of study drug administered at home and throughout the duration of the

clinical study, whether the adverse event is considered related to the treatment or not. Adverse events include the following types of occurrences:

- Adverse reaction: an adverse reaction means any adverse event caused by a drug. Adverse reactions are a subset of all suspected adverse events for which there is reason to conclude that the drug caused the event.
- Suspected adverse reaction means any adverse event for which there is a reasonable possibility that the drug caused the adverse event. Reasonable possibility means there is evidence to suggest a causal relationship between the drug and the adverse event. A suspected adverse reaction implies a lesser degree of certainty about causality than adverse reaction, which means any adverse event caused by a drug. Suspected adverse reactions are the subset of all adverse events for which there is a reasonable possibility that the drug caused the event.
- Other medical experiences, regardless of their relationship to the study drug, such as injury, accidents, increased severity of pre-existing symptoms, apparently unrelated illness, and clinically significant abnormalities in clinical laboratory values, physiological testing, or physical examination findings.
- Reactions from drug overdose, abuse, withdrawal, sensitivity, an interaction with another drug or substance, or toxicity.

Serious Adverse Event (SAE): An adverse event is considered serious if, in the view of either the Investigator or Sponsor, it results in any of the following outcomes:

- Death. This includes any death that occurs during the conduct of a clinical study, including deaths that appear to be completely unrelated to the study drug (e.g., car accidents).
- Life-threatening adverse experience. An adverse event or suspected adverse reaction is considered life-threatening if, in the view of either the Investigator or the Sponsor, its occurrence places the subject at immediate risk of death. It does not include an adverse event or suspected adverse reaction that, had it occurred in a more severe form, might have caused death.
- Persistent or significant disability or incapacity.
- Inpatient hospitalization or prolongation of an existing hospitalization.
- Congenital anomaly or birth defect.
- Other medically important event which, according to appropriate medical judgment, may require medical or surgical intervention to prevent one of the outcomes listed above.

Of note: Surgical procedures or other therapeutic interventions themselves are not adverse events, but the condition for which the surgery/intervention is required is an adverse event and should be documented accordingly.

Elective surgeries and/or treatments requiring hospitalization (e.g., cosmetic surgery), and treatment received at an emergency room or similar facility, will not be considered as SAEs unless one of the definitions of an SAE listed above is met.

Non-Serious Adverse Event: A non-serious adverse event includes any adverse event that is not described in the previous SAE category.

Unexpected: An adverse event or suspected adverse reaction is considered unexpected if it is not listed in the Investigator Brochure or is not listed with the specificity or severity that has been observed. Unexpected, as used in this definition, also refers to adverse events or suspected adverse reactions that are mentioned in the Investigator Brochure as occurring with a class of drugs or as anticipated from the pharmacological properties of the drug, but are not specifically mentioned as occurring with the particular drug under investigation.

8.5.2.1.2 Documentation of Adverse Events

Adverse events that are ongoing from Study HZNP-ACT-302 will be considered baseline signs/symptoms. The TEAE reporting period begins with the date of the first dose of study drug in Study HZNP-ACT-303 and continues until completion of study participation (i.e., the patient is transitioned to the commercially available product, the Sponsor decides not to continue development for the treatment of FA, or the subject prematurely withdraws from the study). All baseline signs/symptoms and TEAEs must be recorded in the source documents and on the subject's eCRF.

If the Investigator observes an SAE after study completion that he/she believes was possibly caused by the study medication, the Investigator will report this SAE using the procedures described in [Section 8.5.2.1.5](#).

Unchanged, chronic conditions are **NOT** considered adverse events and should not be recorded on the adverse event pages of the eCRF unless there is an exacerbation of a chronic condition.

Disease progression can be considered as a worsening of a subject's condition attributable to the disease for which the study drug is being studied (i.e., FA). It may be an increase in the severity of the disease under study and/or increases in the symptoms of the disease. The development of worsening ataxia may be considered as disease progression and not an adverse event. Events, which are unequivocally due to disease progression, should only be reported as adverse events if they fulfill any of the SAE criteria or are the reason for discontinuation of treatment with the study drug.

In addition, hospitalizations for planned procedures are not considered an adverse event unless they are prolonged hospitalizations, and emergency room visits less than 24 hours in duration are not considered hospitalizations.

Detailed information regarding all SAEs must also be recorded on the Serious Adverse Event Reporting Form. Whenever possible, the Investigator should group together into a single term the signs and symptoms that constitute a single diagnosis. For example, cough, rhinitis, and sneezing might be grouped together as “upper respiratory infection” if the Investigator is confident of the diagnosis.

8.5.2.1.3 Grading of Adverse Events

The severity of all adverse events, including all treatment-emergent clinically significant laboratory test results and all treatment-emergent clinically significant changes in laboratory test results, will be assessed in accordance with the following criteria:

- Mild (Grade 1): awareness of signs or symptoms that are easily tolerated, are of minor irritant type, cause no loss of time from usual activities, do not require medication or further medical evaluation, and/or are transient.
- Moderate (Grade 2): signs or symptoms sufficient to interfere with function but not activities of daily living.
- Severe (Grade 3): signs or symptoms sufficient to interfere with activities of daily living; signs and symptoms may be of a systemic nature or may require further medical evaluation and/or treatment.
- Life-Threatening (Grade 4): disabling or with life-threatening consequences. This definition does not include any event that might have caused death if it had occurred in a more severe form.
- Fatal (Grade 5): death related to an adverse event.

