8.5.2.1.6 Follow-Up of Adverse Events

Once the study-defined non-serious adverse event and SAE reporting periods have passed, reporting is required only if an Investigator becomes aware of an SAE that he or she considers related to the study treatment.

After the initial recording of an adverse event, the Investigator should proactively follow the subject. Any ongoing study drug-related adverse event present at the time of study termination, including a clinically significant laboratory test abnormality, will be followed until resolved or until the event stabilizes and the overall clinical outcome has been ascertained.

In the event of unexplained, treatment-emergent, clinically significant abnormal laboratory test results or clinically significant changes in laboratory test results, the tests should be repeated immediately and followed until the values have returned to within the reference range or to baseline for that subject.

The Investigator will document on the adverse event eCRF any/all ongoing non-serious adverse events that will not be followed further after the subject exits the study. If in doubt, the Investigator should consult the sponsor's medical monitor.

All SAEs should be followed until resolution, until the condition stabilizes, or until the subject is lost to follow-up. Once the SAE is resolved, the corresponding adverse event eCRF page should be updated.

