5.4 Hepatic Toxicity

Repeated administration of ACTIMMUNE to patients with advanced hepatic disease may result in accumulation of interferon gamma-1b. Frequent assessment of liver function in these patients is recommended.

Elevations of aspartate transaminase (AST) and /or alanine transaminase (ALT) (up to 25-fold) have been observed during ACTIMMUNE therapy. The incidence appeared to be higher in patients less than 1 year of age compared to older children. The transaminase elevations were reversible with reduction in dosage or interruption of ACTIMMUNE treatment. Patients begun on ACTIMMUNE before age one year should receive monthly assessments of liver function. If severe hepatic enzyme elevations develop, ACTIMMUNE dosage should be modified [see *Dosage and Administration (2.3)*].

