9.2 Clinical Laboratory Evaluations

Descriptive summaries of actual (absolute) values and changes from baseline will be presented for Chemistry, Urinalysis, and Complete Blood Count. These tables will be grouped by visit, and overall treatment.

The number and proportion of subjects with clinical laboratory values below, within, or above normal ranges, at each study visit will be tabulated (shift tables) for each clinical laboratory analyte by treatment group. Normal ranges will be provided by the central laboratory (Eurofins Central Laboratory) used in this study.

Laboratory values will be displayed in data listings and those that are outside the normal range will be flagged, along with the corresponding normal ranges.

Protocol: HZNP-ACT-303 Page 15 of 19

Final Version 1.0

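### Laboratory adverse events have no laboratory grading criteria, and no table described in the SAP counts subjects with marked liver or blood-count abnormality

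*Protocol*

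**What the plan says.** **Grading.** Protocol 8.5.2.1.3 applies one scale to all adverse events, "including all treatment-emergent clinically significant laboratory test results and all treatment-emergent clinically significant changes in laboratory test results, will be assessed" on it.

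- Grade 1 opens with "awareness of signs or symptoms that are easily tolerated, are of minor irritant type, cause no loss of time from usual activities" and closes with "do not require medication or further medical evaluation, and/or are transient".
- Grade 2 is "signs or symptoms sufficient to interfere with function but not activities of daily living".
- Grade 3 leads with interference with daily living and adds that the signs and symptoms may call for further evaluation or treatment.
- Grade 4 is defined by disabling or life-threatening consequences, and Grade 5 is death.

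No grade refers to the size of a laboratory value. For an unexplained, clinically significant laboratory result, Protocol 8.5.2.1.6 says that "the tests should be repeated immediately and followed until the values have returned to within the reference range" or to the subject's baseline.

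**Reporting of adverse events.** SAP 9.1 tabulates TEAEs by severity and keeps the maximum intensity per subject and preferred term. SAP 6.2 imputes a missing severity as Severe.

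**Reporting of laboratory data.** SAP 9.2 plans descriptive summaries by visit, shift tables of subjects with "clinical laboratory values below, within, or above normal ranges, at each study visit", and listings in which out-of-range values are flagged beside the normal range. SAP 6 gives the descriptive statistics, which include minimum and maximum, and restricts unscheduled assessments to listings. SAP 6.2 uses a repeat laboratory result only when the first is missing or invalid.

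**The concern.** Long-term safety is the sole objective, and the SAP drops the efficacy analyses in favour of an abbreviated safety report. The label in Protocol Appendix 16.2 names transaminase elevation, neutropenia and thrombocytopenia as known risks. A reader of the report will want to know how many subjects had a marked abnormality of these kinds.

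Neither route described in the plan gives that number. The severity table depends on a scale that does not ask how abnormal the value was. The shift tables ask only which side of the normal range it fell on. Results from extra samples taken between the six-monthly laboratory visits, when a suspected toxicity is most likely to be followed up, do not enter the summaries.

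**Working it through.** The plan has no figure to reproduce: there is no power calculation and no hypothesis test. The check compares the texts and adds a small illustration.

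**1. Which grade fits a clinically significant ALT rise or low neutrophil count without symptoms?**

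| Grade | Basis | Fit |
|---|---|---|
| 1 | Tolerated, no further evaluation needed, and/or transient | Possible, but strained if the result needs evaluation |
| 2 | Interferes with function | Not met on its wording |
| 3 | Interferes with daily living; may need evaluation or treatment | Lead criterion not met; the second clause can be read to fit |
| 4 | Disabling or life-threatening consequences | Possible when consequences are that serious |

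Two sites could reasonably assign Grade 1 and Grade 3 to the same value. A site that finds no fitting grade and leaves the field blank produces a Severe event under SAP 6.2.

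**2. What does the shift table show?** Assume an upper limit of normal (ULN) of 1. Values of 1.05, 2, 5 and 25 × ULN all fall in the above category. A subject who goes from 1.05 to 25 × ULN is tabulated as above-to-above, so no shift appears. This can arise here because SAP 6.3 takes baseline from the Week 26 visit of HZNP-ACT-302, which the protocol describes as the last on-treatment visit. A subject may therefore already be out of range at baseline.

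**3. What do the descriptive statistics add?** All inputs are assumptions: every other subject is at 0.5 × ULN, and n runs from 14 to 90.

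- One subject at 25 × ULN, n = 14: mean = (13 × 0.5 + 25)/14 = 31.5/14 = 2.25; median 0.5; maximum 25.
- One subject at 25 × ULN, n = 90: mean = (89 × 0.5 + 25)/90 = 69.5/90 = 0.77; median 0.5; maximum 25.
- One subject at 1.05 × ULN instead: the maximum is 1.05, so the maximum does separate marked from trivial.

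The maximum does not count subjects. With n = 14, compare two cases:

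- One subject at 25 and one at 1.05: two subjects above, maximum 25, mean = (12 × 0.5 + 26.05)/14 = 2.29.
- Two subjects at 25: two subjects above, maximum 25, mean = (12 × 0.5 + 50)/14 = 4.00.

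The shift category and the maximum are the same in both. Only the mean and SD differ, and in real data they cannot be turned back into a count.

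**4. Which values enter the summaries?** Protocol 8.5.2.5 schedules samples at baseline, each six-month visit and end of study, with extra samples as clinically indicated. Under SAP 6 and 6.2, unscheduled results and most repeats are excluded from the by-visit tables. A peak found between visits then appears in the listings but not in the maximum.

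**The case against.** Several points on the other side stand, and they limit the claim.

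- **A reader might infer that no asymptomatic abnormality can be graded.** The documents do not support this. Protocol 8.5.2.1.1 counts an abnormal laboratory finding as a sign, a transient one can be Grade 1, and Grade 4 depends on consequences. The difficulty lies in the middle grades. The instruction to repeat tests covers only unexplained results, and a repeat test need not count as further medical evaluation.
- **A reader might infer that marked toxicity could not be told from trivial change.** That is also too strong. By-visit minima and maxima and the flagged listings show extreme values. Only abnormalities that the investigator judges clinically significant become adverse events. Serious cases can also surface as SAEs, withdrawals, or dose adjustments with recorded reasons, and through the ongoing review by the medical monitor. The count can be made by hand from the listings.
- **The label's fold-rises do not measure the effect here.** The 2-fold to 25-fold elevations in label section 6.2 are relative to baseline, in patients treated before one year of age, whereas the SAP age categories start at 10. They are not multiples of the upper limit in this population. The 25 in the illustration is only an assumed value.
- **The label's advice on severe enzyme elevations concerns treatment decisions** and gives no numeric definition of severe. End-of-study tables are not the means of acting on it, so the point does not rest on it.
- **The full table list cannot be checked.** The list of shells announced in SAP 12 is not visible in the available text. The gap is in what SAP 9.2 describes.

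None of this supplies a described table that counts subjects by degree of abnormality, or brings unscheduled peaks into a summary.

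**Conclusion.** The point holds as a reporting gap with a related ambiguity in grading. The severity of a laboratory adverse event without symptoms depends partly on the site's reading of a scale that has no laboratory criteria. The number of subjects with marked hepatic or haematologic abnormality is not tabulated in the SAP as described and would have to be recovered by hand.

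Its size cannot be expressed as a bias or a rate, because the documents give no expected incidence in this population. The information is collected and listed, so no data are lost and no planned analysis is invalid. The change is still worth making because the missing count bears directly on the study's only objective.

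The conclusion assumes that the unseen shells contain no threshold table. It also assumes that the chemistry panel includes AST and ALT and that the blood count includes a neutrophil count. Protocol 8.5.2.5 names the panels but not the analytes.

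**What to change.** In SAP 9.2, add one table of subjects by:

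- highest post-baseline AST and ALT in multiples of the upper limit of normal (for example >1–3, >3–5, >5–10 and >10; these cut-offs are illustrative);
- lowest post-baseline neutrophil and platelet count, in bands.

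Fix the cut-offs before database lock. State that unscheduled and repeat values are included, as an explicit exception to SAP 6 and 6.2. Without that sentence the table would miss the values most likely to matter. Under the assumption on analytes above, the cost is one table from data already collected.

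Optionally, add to Protocol 8.5.2.1.3 that adverse events which are laboratory abnormalities are graded by the size of the abnormality, with the present scale kept for all other events. The drawback is a possible mismatch with grading in the parent studies, if they used the same scale. The SAP table supplies the missing count even if the protocol is not reopened.

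Both changes concern grading and reporting only and imply no dosing rule.

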8.5.2.1.4 Relationship to Study Drug

The relationship of the study drug to each adverse event will be determined by the Investigator based on the following definition:

- No reasonable causal relationship (probably not related): There is no plausible temporal relationship or there is another explanation that unequivocally provides a more plausible explanation for the event.
- Yes, reasonable causal relationship (possibly related): There is evidence in favor of a causal relationship; i.e., there is a plausible time course, and at least one of the following criteria apply:
 - There is a reasonable pharmacological relationship (or known class effect)
 - There is no other more plausible explanation

- There is a positive de-challenge (without active treatment of the event)
- There is a positive re-challenge
- There is a distinguishable dose effect

Within the reporting requirement under 21 CFR 312.32(c)(1)(i), the FDA provides the following examples of types of evidence that would suggest a causal relationship between the drug and the adverse event.

- A single occurrence of an event that is uncommon and known to be strongly associated with drug exposure (e.g., angioedema, hepatic injury, Stevens-Johnson Syndrome).
- One or more occurrences of an event that is not commonly associated with drug exposure, but is otherwise uncommon in the population exposed to the drug (e.g., tendon rupture).
- An aggregate analysis of specific events observed in a clinical trial (such as known consequences of the underlying disease or condition under investigation or other events that commonly occur in the study population independent of drug therapy) that indicates those events occur more frequently in the drug treatment group than in a concurrent or historical control group.

